Protocol Title: An Exploration of a Prime-Boost Approach for Universal Influenza Vaccination: Immunogenicity and Safety Study of a H5N1 Influenza Vaccine in Prior Recipients of Live Attenuated H2N2, H6N1 and H9N2 Influenza Vaccines and in H5N1 and Live Attenuated Vaccine Naïve Individuals

Protocol Version: V. 3.0
April 12, 2019

Revision History:

Protocol Version	Date
1.0	6 November 2018
1.1	19 November 2018
1.2	10 December 2018
2.0	27 February 2019

Subjects: Healthy male and non-pregnant female subjects 18-60 years of age

Number of Subjects: Approximately 32-35

Trial Design: Open-label outpatient trial of 1 dose of H5N1 pISV

Immunization Schedule:

Cohort	Number of Subjects	Previous Vaccine	Number of doses of inactivated H5N1 vaccine
1	12-15	2 doses of pandemic live attenuated influenza vaccine (pLAIV) H2N2, H6N1 or H9N2	1
2	20	Naive	1

Product Description: Monovalent Influenza H5N1 Subvirion Vaccine (A/VietNam/1203/04 (H5N1, clade 1) vaccine, lot number UD08916

1. INTRODUCTION

1.1 Background: Pandemic Influenza

Influenza is a negative-sense, single-stranded RNA virus belonging to the family *Orthomyxoviridae* that consists of 4 genera: influenza A, influenza B, influenza C, and Thogoto viruses. The proteins of influenza A are encoded by genes on 8 RNA segments. Influenza A viruses are widely distributed in nature and can infect a wide variety of birds and mammals, including humans. Influenza A virus subtypes are classified on the basis of the antigenicity of their surface glycoproteins, hemagglutinin (HA) and neuraminidase (NA).

Sixteen HA subtypes and 9 NA subtypes of influenza A viruses have been identified that infect birds. Waterfowl are the natural reservoir of avian influenza (AI) viruses. Most AI infections in birds are not associated with overt disease, and the viruses are generally thought to be in evolutionary stasis in these hosts. This is in contrast to influenza A viruses in the human population where relatively few subtypes have caused sustained outbreaks of disease: viruses bearing H1, H2, and H3 HA and N1 and N2 NA genes have circulated in the human population throughout the 20th century. H1N1 viruses first appeared in 1918 and circulated until 1957 when they were replaced by H2N2 viruses. These in turn were replaced in 1968 by H3N2 viruses that continue to circulate at the present time. In 1977, H1N1 viruses reappeared and have continued to co-circulate with the H3N2 viruses. The H1N1 virus circulating previously was replaced by the 2009 pandemic H1N1 virus. Influenza A and B viruses cause epidemics in humans each winter.

As seen in 2009, in addition to the seasonal influenza epidemics, the potential also exists for an influenza pandemic at any time. This occurs when an influenza strain with a novel HA subtype (with or without a novel NA subtype) appears in the human population. In the 20th century, pandemics occurred in 1918, 1957, and 1968, and were associated with significant morbidity and mortality (1). The 2009 H1N1 pandemic caused approximately 10,000 deaths in the United (2), 95% of whom were under the age of 65. It is estimated that, in the United States alone, the next influenza pandemic could cause 89,000 to 207,000 deaths, and 314,000 to 734,000 hospitalizations, as well as tens of millions of outpatient visits and illnesses, depending on the severity of the pandemic (3).

During the 2009 H1N1 pandemic, robust antibody responses to the HA stalk epitope were detected following infection or vaccination. This led Li and colleagues to propose that rare B cells directed against the conserved stalk epitope were amplified because the immunodominant head region of the HA was novel (4). Pandemic H1N1 influenza vaccine induces a recall response in humans that favors broadly cross-reactive memory cells. Subsequently, Krammer and Palese have proposed that sequential immunization with influenza viruses bearing chimeric HAs with a conserved HA stalk and different HA head domains will amplify the antibody response to the HA stalk (5).

In three independent clinical trials, we have demonstrated that pandemic live attenuated influenza vaccine (pLAIIV) establishes long lasting immune memory that is detected

when pLAIIV recipients receive a dose of pandemic inactivated subvirion vaccine (pISV) (6-8).

However, we have not administered a pISV bearing group 1 HA to pLAIIV recipients of a mismatched group 1 pLAIIV. We have administered a group 1 pISV (H5N1 VN04) to recipients of an H7N3 pLAIIV and a group 2 pISV (H7N7 Netherlands03) to recipients of an H2N3 pLAIIV(6, 7). We have previously administered group 1 pLAIIVs (H2N2, H6N1, H9N2) to study subjects in Baltimore (9-11). This study will examine the effect of a group 1 pISV (H5N1 VN04) vaccine to previous recipients of a different group 1 pLAIIV recipients (H2N2, H6N1 and H9N2).

1.2 Vaccine Description

Monovalent Influenza Subvirion Vaccine (H5N1) is an inactivated unadjuvanted influenza vaccine. The vaccine is a sterile suspension prepared from influenza virus propagated in embryonated chicken eggs. The vaccine is manufactured by Sanofi Pasteur Inc., Swiftwater, PA. The virus-containing fluids are harvested and inactivated with formaldehyde. The influenza virus is concentrated and purified in a linear sucrose density gradient solution using a continuous flow centrifuge. The virus is then chemically disrupted using a nonionic surfactant, polyethylene glycol p-isoctylphenyl ether (Triton® X-100), producing a “split virus”. The split virus is then further purified by chemical means and suspended in sodium phosphate-buffered isotonic sodium chloride solution. The vaccine is formulated to contain 90 µg HA per 1.0 mL of the influenza virus strain A/Viet Nam/1203/04 (H5N1, clade 1). Porcine gelatin (500 µg per 1.0 mL) is added as a stabilizer. Thimerosal, a mercury derivative, is added as a preservative to a concentration of not more than 98.2 µg thimerosal per 1.0 mL (approximately 50 µg mercury per 1.0 mL). The vaccine may also contain residual amounts of formaldehyde (not more than 200 µg per 1.0 mL), polyethylene glycol p-isoctylphenyl ether (not more than 0.05%), and sucrose (not more than 2.0%). We will be administering 0.5 mL, or 45 µg HA per each subject.

The vaccine is provided as a suspension in 5 mL multi-dose vials and should be administered as an intramuscular (IM) injection. The vaccine should be stored between 2 to 8°C. The vaccine should not be frozen.

The vaccine is licensed for active immunization of persons 18-64 years of age at increased risk of exposure to the H5N1 influenza virus subtype contained in the vaccine. The clinical trial material for this study is a lot prepared specifically for investigational use, lot number UD08916. The vaccine will be provided by the Biomedical Advanced Research and Development Authority (BARDA), U.S. Department of Health and Human Services (DHHS). The product label is provided in [Appendix D](#).

1.3 Clinical Experience with the H5N1 inactivated vaccine

A prospective, randomized, double-blinded, placebo-controlled, dose-ranging Phase 1-2 study was conducted in 451 healthy subjects aged 18-64 years (12). The vaccine was well tolerated. Mild pain at the injection site was the most common adverse event (AE) for all

doses of vaccine evaluated (90, 45, 15, or 7.5 μ g). The number of subjects with an antibody response was highest among those who received two doses of 90 μ g of vaccine: HI titers of $\geq 1:40$ were observed in 58% of subjects in this group, and 54% of subjects in this group had microneutralization assay (MN) titers of $\geq 1:40$. This vaccine was subsequently licensed for use in healthy adults aged 18-64 years of age at increased risk of H5N1 influenza infection (

Appendix C: H5N1 Vaccine Product Insert).

1.4 Rationale

Unadjuvanted inactivated H5N1 vaccines have been shown to be poorly immunogenic in humans, whether administered as inactivated or live attenuated vaccines (12, 13).

Previously, it has been demonstrated that subjects who were primed with an inactivated H5N1 vaccine and then several years later receive another inactivated H5N1 vaccine developed significantly greater HI and MN antibody titers than unprimed subjects (14, 15).

In 2006 and 2007, the safety, infectivity and immunogenicity of 2 live attenuated H5N1 vaccines, H5N1 VN 04 cold-adapted (*ca*) and H5N1 HK 03 *ca*, were evaluated in healthy adults (13). Nineteen subjects received 2 doses of $10^{7.5}$ 50% tissue culture infectious dose (TCID₅₀) of H5N1 VN 04 *ca*. Of these subjects, 15 had vaccine virus detected by real-time reverse transcriptase polymerase chain reaction (rRT-PCR) after either dose, however, only 10% of subjects had measurable antibody responses by HI assay, and 5% by MN assay. Fifty two percent of subjects had measurable anti-H5 serum immunoglobulin A (IgA) antibodies. Sixteen subjects received 2 doses of $10^{7.5}$ TCID₅₀ of H5N1 HK 03 *ca*. Vaccine virus was detected by rRT-PCR in 12 subjects after either dose, and none of the subjects had measurable HI or MN antibodies after vaccination. Three subjects had increases in serum anti-H5 serum IgA.

When the inactivated, unadjuvanted H5N1 subvirion vaccine was evaluated in healthy adults, 2 doses of 90 μ g of vaccine were required to elicit a 4-fold or greater rise in either HI or MN titer against the A/Vietnam/1203/2004 (H5N1) virus in the majority of subjects (12). Other unadjuvanted H5N1 vaccines were also poorly immunogenic (reviewed in (16)). Inactivated and virosomal H5N1 vaccines, while poorly immunogenic, do elicit stalk antibody responses (17, 18).

Although initial immunization with the unadjuvanted inactivated H5N1 vaccine or with live attenuated H5N1 vaccines generally induced inadequate antibody responses, some data suggest that immune priming may occur which is only revealed when individuals are revaccinated with H5 vaccine. For example, Goji et al. demonstrated that subjects who had received a clade 0 inactivated H5N1 vaccine (derived from A/Hong Kong/156/97) were primed to respond years later to a clade 1 H5N1 vaccine (derived from A/VietNam/1203/04), and that their antibody responses to the clade 1 vaccine were substantially greater than those observed in H5-naïve subjects (14).

Previously we sought to determine whether the H5N1 VN 04 *ca* and H5N1 HK 03 *ca* vaccines induced subclinical priming that could be revealed when subjects who received these vaccines are immunized with the inactivated H5N1 subvirion vaccine. We found that use of the H5NI subvirion vaccine increased frequency of antibody response 82% by the hemagglutination inhibition assay and displayed a significantly higher antibody titer of 112 compared to 76 in naïve subjects. The affinity of antibody and breadth of cross-clade neutralization was also enhanced in the primed subjects.

We found (Table 1 below) that the head-specific antibody (Ab) response in pLAIIV prime-pISV boost scenarios is not affected by the interval between pLAIIV prime and pISV boost. We saw similar percent seroconversion and geometric mean titers (GMTs) in 3 independent clinical trials with different pLAIIV/pISV pairs administered at different intervals, from 3 months to 56 months (6-8).

Table 1: Antibody Titers After pLAIIV pISV Prime Boost Studies

pLAIIV		pISV	Interval pLAIIV- pISV	HAI Ab titer following receipt of pISV					
Vaccine	# doses			n	GMT (range)	Responders			
					%	GMT			
H5N1 VN04	2	H5N1 VN04	56 m	11	48 (5-1280)	64	165		
H7N7 NL03	2	H7N7 NL03	19-24 m	13	34 (2-1024)	69	119		
H7N9 Anhui/13	2	H7N9 Anhui/13	3 m	14	74 (2-512)	79	175		

HAI = hemagglutination inhibition assay

We have evidence that pLAIIV primes for a stalk-specific response (19, 20). However, in each of our prime-boost studies, the inactivated vaccine boost that recalled the response primed by the pLAIIV was matched for the HA head and as Halliley et. al. and Henry Dunand et. al. have shown, this approach boosts the head-specific antibodies to a much greater extent than the stalk-specific antibodies (19, 20). In the proposed study, our objective is to determine whether boosting with an inactivated vaccine bearing a mismatched head, but shared stalk will boost the stalk response preferentially. Preclinical studies have demonstrated that prime-boost strategies using influenza viruses with mismatched HA heads and conserved stalks boost the antibody response to the HA stalk (21, 22).

All participants in the study will have been exposed to group 1 stalk via exposure to H1N1pdm09 viruses since 2009. However, the subjects that received pLAIIV 5-10 years ago differ from the control cohort in having received two doses of a different group 1 virus (H2N2 or H6N1 or H9N2) followed by interim exposure to H1N1pdm09 viruses and vaccines.

The first-time people were vaccinated against H1N1pdm09, they had a very robust stalk-specific response, presumably because the HA head was novel, and the stalk was conserved. However, on revaccination, the head-specific response became dominant and the stalk-specific response was not detected (23). These findings are consistent with Ellebedy et. al. findings that there was no rise in stalk-specific antibody titers over a 4-year period from 2010 to 2014 (18). The data from these studies indicate that (1) although stalk-specific immunoglobulin G (IgG) + memory B cells are detectable, they are minimally boosted by seasonal influenza vaccine that contains the H1N1pdm09 HA and (2) over time and re-exposure, the head-specific response dominates over the stalk-specific response.

The data from Ellebedy et. al. (18) suggest that it is likely that the H5N1 pISV will induce a stalk-specific response in the control cohort as well as the pLAIIV primed subjects, but we hypothesize that recipients of the H2N2, H6N1 and H9N2 pLAIIVs will have more memory B cells against the group 1 stalk than the control cohort because they differ from the control cohort in having received two doses of a different group 1 virus (H2N2 or H6N1 or H9N2). It is now 9 years since the emergence of the 2009 pandemic H1N1 virus and people would have been exposed to the virus or vaccine more than once so they will have a predominantly head-specific response to H1N1pdm09 as reported by Andrews et. al. (23).

Additionally, Yassine et. al. (24), reported that not all broadly neutralizing antibodies are created equal; using stalk stabilized probes against H1 seasonal, H1 pdm09, H2, H5 and H9 HA stems, they found that ~45% of 202 people had antibodies that bound the stalks of non-circulating viruses (H2, H5, H9) and 30% had antibodies that bound 4 of the 5 probes. They reported that sera collected either prior to the 2009 pandemic or afterwards showed no differences in cross-reactivity and they observed no difference in the profiles of cross-reactive sera from vaccinated and non-vaccinated subjects collected after the H1N1 pandemic emergence. However, there was a statistically significant boost in specific stalk antibody titers to H1 CA 09 HA SS probe in subjects that received pandemic H1N1 influenza vaccine compared to those that did not receive the vaccine within the same time period. They also noted a higher rate of cross-reactive antibodies in the older population, especially those born within or before the period of H2N2 pandemic (24).

We will use similar probes (25) to detect stalk antibodies in the sera from this trial and hypothesize that on administration of an H5N1 inactivated vaccine, we will see a stalk-specific antibody response in both cohorts but the magnitude of the response and the breadth of the stalk antibody response in the pLAIIV primed subjects will be greater than in the controls.

In summary, we hypothesize that people that have been primed with pLAIIVs bearing novel HAs will develop antibodies that react more broadly than people whose only exposure to a novel HA head was H1N1pdm09.

1.5 Participation of Children

It is felt that insufficient data are available to judge the potential risk in children. As such, children will not be enrolled in this study. In addition, to date, children have not received the H2, H6 or H9 *ca* vaccines.

1.6 Statement of Compliance

This trial will be conducted in compliance with the protocol, International Conference on Harmonisation/Good Clinical Practice (ICH/GCP) guidelines, Food and Drug Administration (FDA) regulations (21 Code of Federal Regulations [CFR]), and the Johns Hopkins Bloomberg School of Public Health Institutional Review Board.

1.7 Hypothesis

Recipients of the H2N2, H6N1 and H9N2 pLAIVs will have more memory B cells against the group 1 stalk than the control cohort, whose only exposure to a novel HA head was H1N1pdm09. Therefore, the magnitude of the response and the breadth of the stalk antibody response in the pLAIV primed subjects will be greater than in the controls following administration of an H5N1 inactivated vaccine.

2. OBJECTIVES

2.1 Primary Objective:

To explore the difference in the stalk antibody response against Influenza A group 1 stalks as measured by enzyme-linked immunosorbent assay (ELISA) and neutralization titer after receipt of the Monovalent Influenza Subvirion Vaccine (H5N1) in previous recipients of H2N2, H6N1 and H9N2 pLAIVs compared with healthy, pLAIV-naïve individuals.

2.2 Secondary Objective:

Assess the reactogenicity of the Monovalent Influenza Subvirion Vaccine (H5N1) in previous recipients of live attenuated influenza vaccine (LAIV) compared with healthy, pLAIV-naïve individuals.

Adverse events will be assessed, graded and recorded for 28 days after vaccination. Serious Adverse Events (SAEs) will be assessed for 90 days after the immunization.

2.3 Exploratory Objectives:

- To assess the biological activity of antibodies to the HA stalk region by passive transfer of serum from study subjects to mice to assess their ability to protect the mice from lethal challenge with an influenza virus.
- To correlate ELISA and neutralizing stalk antibody titers with functional ability of the post vaccine serum to protect mice from lethal challenge.
- To assess the breadth of the vaccine induced antibody response.
- To assess plasmablast and memory B cell responses to the pISV in the previous pLAIV recipients compared with naïve individuals.
- To assess the longevity of the stalk antibody response.
- To determine the titer of anti-H5 head antibodies in the 2 cohorts of subjects.
- To determine the titer of antibodies directed to the HA head received in the pLAIV doses.

3. STUDY DESIGN

3.1 Summary

This open-label, outpatient, exploratory study will recall study subjects who previously received a group 1 pLAIV (H2N2, H6N1 or H9N2) and administer 1 dose of pISV (e.g. H5N1 pISV) to determine whether the HA stalk antibody response is amplified following administration of pISV H5N1 with a mismatched HA head and conserved HA stalk.

A control cohort of naive subjects will receive H5N1 pISV.

All subjects will be followed for approximately 360 days after receipt of the H5N1 pISV.

3.2 Study Schedule

The study will be divided into 3 phases:

1. Screening, eligibility determination and consent up to 60 days prior to vaccination/enrollment (usually 2 visits initiated under a separate institutional review board (IRB)-approved screening protocol)
2. Vaccination/Enrollment (Day 0)
3. Outpatient follow-up at 7, 14, 28, 56, 90, and 360 days post vaccination

3.3 Study Procedures

(See Section 6 for detailed description of study procedures)

3.4 Sample Size

Up to 35 healthy adults will be selected to receive 1 dose of H5N1 pISV. Up to 15 of these subjects will have previously received group 1 pLAIWs (H2N2, H6N1 or H9N2), and 20 of these subjects will be naïve. More than 35 subjects may be consented, vaccinated and enrolled (see Replacement of Subjects) if necessary to achieve enrollment goals. The Medical Monitor/Safety Office and the Clinical Trials Monitor will be notified promptly by email in advance if the study team anticipates that study vaccinations will exceed 38 subjects per replacement procedure.

3.5 Treatment assignment

All subjects enrolled in the study will receive 1 dose of H5N1pISV

3.6 Duration of Participation

Duration of individual subject participation in the trial is approximately 360 days from time of vaccination (not including 1 – 2 screening visits prior to enrollment) and will consist of a vaccination/enrollment visit and 6 follow up visits. The duration of the study, from the time of the first subject vaccination to the end of the last subject study visit, is estimated to be approximately 18 months.

4. SELECTION OF STUDY SUBJECTS

Individuals who previously received H2N2, H6N1, or H9N2 pLAIW as participants in CIR vaccine studies and who indicated they would be willing to participate in future studies, will be contacted and invited to participate in this study, as described in Section 6. Healthy subjects will be recruited from the general population for the LAIV negative controls.

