4.1 Inclusion Criteria

All the following criteria must be met for a subject to be enrolled in this trial:

1. Adult males and non-pregnant females between 18 years and 60 years of age inclusive.
2. General good health, without significant medical illness, physical examination findings, or significant laboratory abnormalities as determined by the investigator.
3. Available for the duration of the trial.

4. Able to demonstrate understanding of key study concepts, study rationale, and study participation requirements by scoring $\geq 70\%$ on a written comprehension assessment in ≤ 3 attempts.
5. Willingness to participate in the study as evidenced by signing the informed consent document.
6. Willingness to allow storage and testing of laboratory samples for future research.
7. Received 2 doses of live attenuated H2N2, H6N1, or H9N2 vaccine in a prior trial (Cohort 1) or H2N2, H6N1 and H9N2 naïve (Cohort 2)
8. Willingness to forego seasonal influenza virus vaccination from 1 month before vaccination until 3 months after vaccination.
9. Female subjects of childbearing potential must agree to have used effective birth control methods beginning at least one month prior to vaccination, and continuing with ‘per label/fully effective use’ for the chosen method for duration of the study, from amongst these:
 - pharmacologic/hormonal contraceptives, including oral, parenteral, subcutaneous, and transcutaneous delivery;
 - condoms with spermicide;
 - diaphragm with spermicide;
 - intrauterine device;
 - absolute abstinence from heterosexual intercourse as a matter of normal preferred lifestyle;

or must be surgically sterile or must be age 50 AND have had no menses at all for at least one full year.

All females must provide urine for pregnancy testing prior to enrollment (immediately prior vaccination), as well as a statement of menstrual history and a summary of all potentially reproductive sexual activity for the month prior to vaccination, and at each study contact throughout the study, and report known or suspected pregnancy immediately.

10. Willingness to refrain from blood donation during the course of the study.

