1. Seropositive to the H5N1 influenza A virus (serum hemagglutination inhibition assay (HAI) titer $>1:8$).
2. Have previously received an investigational LAIV in another study.

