6.2 Recruitment

The CIR disseminates information about opportunities to participate in its vaccine clinical trials via IRB-approved content on its own website (centerforimmunizationresearch.org), social media platforms, YouTube, and in web, newspaper, radio and television advertisements. Study specific IRB-approved fliers and brochures are distributed locally.

Cohort 1 will consist of prior recipients of Live Attenuated H2N2, H6N1 and H9N2 Influenza Vaccines as participants in previous CIR studies (CIR 211, CIR 247, CIR 251). With each initial and subsequent telephone contact, subjects are asked if they will allow us to call them about opportunities to participate in future studies. The response to this question is documented on a pre-screening assessment form and in the CIR Adult Studies Data Base. Study staff has compiled a list of approximately 63 volunteers who participated in these three studies from 2005 - 2009. They will be contacted via phone, and/or IRB-approved letter, and invited to participate in our general screening study to see if they would be eligible and willing to participate in this study as recalled subjects. After this initial contact, subjects will be referred to the telephone recruiter. The recruiter will administer a brief qualifying phone screen after obtaining verbal consent and eligible recruits will be scheduled for in-person screening visits according to their interests and availability.

Cohort 2 – the control cohort consisting of LAIV-naïve/H5 antibody negative subjects, will be identified as individuals who make inquiries by telephone call or email to the clinical trial site. A telephone recruiter will respond to calls and emails and provide brief scripted descriptions of currently accruing CIR trials as specified in the CIR’s general screening protocol. The recruiter will administer a brief qualifying phone screen after obtaining verbal consent and eligible recruits will be scheduled for in-person screening visits according to their interests and availability.

The screening evaluation outlined below will be completed within 60 days prior to vaccination. During the initial in-person screening visit trained study staff will:

1. Provide a copy of the screening study consent form and encourage the volunteer to read the consent and ask questions
2. Administer a brief, written comprehension assessment to confirm understanding of the screening study procedures and requirements

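### The non-randomised primary comparison is neither matched nor adjusted for age, and age or birth cohort could bias it in either direction

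*Combined protocol and SAP*

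**What the plan says.** **Who is compared.** Cohort 1 is recalled from earlier trials. Section 6.2 describes a list of "approximately 63 volunteers who participated in these three studies from 2005 - 2009". For Cohort 2, section 4 says "Healthy subjects will be recruited from the general population for the LAIV negative controls", and section 6.2 takes them from people who contact the site.

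**Age.** One criterion in section 4.1 covers both cohorts: "Adult males and non-pregnant females between 18 years and 60 years of age inclusive". Section 1.5 says that children have not received the H2, H6 or H9 vaccines. Section 1.4 puts receipt of pLAIV five to ten years before this study, which does not agree with the 2005-2009 dates.

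**What naïve means.** Criterion 7 in section 4.1 describes controls as "H2N2, H6N1 and H9N2 naïve (Cohort 2"). Section 6.2 calls them "the control cohort consisting of LAIV-naïve/H5 antibody negative subjects". The only influenza serology that excludes a control is in section 4.2: "Seropositive to the H5N1 influenza A virus".

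**Age and the biology.** Of the survey of stalk antibody that it cites, section 1.4 says: "They also noted a higher rate of cross-reactive antibodies in the older population, especially those born within or before the period of H2N2 pandemic". Section 1.1 dates the exposure: H1N1 viruses "circulated until 1957 when they were replaced by H2N2 viruses. These in turn were replaced in 1968 by H3N2 viruses".

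**Analysis.** The primary endpoint in section 10.4 is the fold rise in group 1 stalk antibody by ELISA and microneutralisation. Log titres are compared by t-test or ANOVA. No section provides for matching, age strata, an age covariate or an age sensitivity analysis.

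**The concern.** Without randomisation, the between-cohort difference can be credited to pLAIV only if the cohorts are alike in other determinants of the stalk response. The protocol names one such determinant in its rationale and then does not carry it into recruitment or analysis.

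Two features make imbalance plausible. The lower age limits differ by construction, because Cohort 1 received its vaccine years ago. In addition, a small cohort drawn from about 63 candidates may have a quite different share of people born by 1968 from a control group of general volunteers. Section 1.7 assumes that controls have met only one novel HA head, H1N1pdm09. People who lived through H2N2 circulation may not fit that description, and H2N2 is one of the priming subtypes.

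The between-cohort contrast is the only primary question. A difference, or the lack of one, could reflect age structure, and a confidence interval around a confounded estimate carries the same bias as a test.

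**Working it through.** **1. Age floor of Cohort 1.** Inputs: trials in 2005-2009 (section 6.2); entry age of at least 18, inferred from section 1.5; vaccination in 2018 or 2019 (version 1.0 is dated November 2018 and version 3.0 April 2019).

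Minimum age = 18 + (vaccination year − prior-trial year).
- Prior vaccination in 2009: 18 + 9 = 27 in 2018, and 18 + 10 = 28 in 2019.
- Prior vaccination in 2005: 31 in 2018 and 32 in 2019.
- With the five-to-ten-year interval in section 1.4: 18 + 5 = 23.

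With a floor of 28, controls aged 18-27 have no possible counterpart. That is 10 of the 43 eligible age-years, 18 to 60 inclusive.

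**2. H2N2-era band.** Born by 1968 means aged at least 2018 − 1968 = 50, or 2019 − 1968 = 51. The band of about 51-60 is open to both cohorts.

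**3. The plan's own power figure.** Section 10.2 claims 80% power at alpha 0.05 for a 2-fold higher response with 15 pLAIV subjects. Section 10.1 gives 20 controls. No SD is stated and sidedness is not given, so I took the test as two-sided.

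Noncentrality = Δ / [SD × √(1/n₁ + 1/n₂)], with Δ = log2(2) = 1. Solving for 80% power by the noncentral t gives SD = 1.014 log2:
- standard error = 1.014 × √(1/15 + 1/20) = 0.346;
- noncentrality = 1/0.346 = 2.89; df = 33; critical t = 2.035; power = 80%.

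The same SD with 12 versus 20 and a 2.1-fold ratio (Δ = 1.070) also gives 80%. The two statements agree with each other, but the SD is recovered from them and not verified.

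**4. What a bias would do.** The size of any bias is an assumption. For example, a 30-point difference between cohorts in the share born by 1968, with a 2-fold effect of that exposure on fold rise, gives 0.30 × log2(2) = 0.30 log2 (1.23-fold). Noncentrality is 0.30/0.346 = 0.87.

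| Assumed bias, log2 | Ratio | Two-sided rejection under the null, 15 vs 20 |
|---|---|---|
| 0 | 1.00 | 5% |
| 0.10 | 1.07 | 6% |
| 0.25 | 1.19 | 11% |
| 0.30 | 1.23 | 13% |
| 0.50 | 1.41 | 29% |

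If the bias runs against pLAIV instead, power for a true 2-fold effect falls from 80% to 71% at 0.10, 56% at 0.25 and 29% at 0.50.

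**5. What adjustment or restriction costs.** For a linear model with age, standard error = SD × √(1 − ρ²) × √[(1/n₁ + 1/n₂)/(1 − R²)]. Here ρ is the correlation of age with response. R² = d²p(1 − p)/[1 + d²p(1 − p)], with d the age difference between cohorts in SDs and p = 15/35. All values of ρ and d are assumed.

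| Age difference d | ρ = 0 | ρ = 0.3 | ρ = 0.5 |
|---|---|---|---|
| 0 | 80% | 84% | 90% |
| 0.5 SD | 78% | 81% | 88% |
| 1 SD | 71% | 75% | 83% |

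For the overlapping-age analysis, uniform control ages would leave 20 × 33/43 = 15.3, about 15 controls. With 15 versus 15, noncentrality is 2.70, df = 28, and power is 74%.

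**The case against.** Several objections have force.

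- **Cohort 1 also runs to 60.** A reader might infer that older controls, naturally primed by H2N2, dilute the contrast. On uniform ages the 51-60 share of controls is 10/43 = 23%. If they all responded like pLAIV recipients, a 2-fold effect would become 2^(1 − 0.233) = 1.70-fold and power would fall to 58%. The documents do not support using that figure. It assumes that H2N2-era controls respond exactly as primed subjects do and that older Cohort 1 members gain nothing extra. It also describes dilution, not confounding. Under the same assumptions, matching controls to ages 28-60 would raise their primed share to 10/33 = 30% and lower power further, to 50% (1.62-fold). If H2N2 exposure instead doubled the response in both cohorts, the net bias would be 0.303 − 0.233 = 0.07 log2 in favour of Cohort 1, and rejection under the null would move only from 5.0% to 5.4%.
- **The cited age effect is on prevalence.** The endpoint is fold rise, which removes differences in level. It does not remove an age-dependent recall response or a ceiling from high baseline titres, but neither is quantified in the documents.
- **Criterion 7 most naturally means vaccine-naïve.** It is paired with receipt of pLAIV, and the title and sections 2.1 and 6.2 use vaccine-naïve terms. The lack of H2 serology is therefore not a failure to verify a criterion.
- **The study is exploratory** (section 10.1), and stored pre- and post-pLAIV sera (section 6.10) give Cohort 1 a partial within-subject reference. But section 10.2 states a null hypothesis, alpha and power, and controls have no such sera.

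These objections limit the size and direction of the claim. They leave the lack of matching and adjustment unanswered.

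**Conclusion.** Age and birth cohort are potential confounders of the primary comparison that the plan itself identifies and does not address. The structural part is the difference in lower age limits: about 27-28 for Cohort 1 against 18 for controls. That floor rests on the 2005-2009 dates and an inferred adult entry age. It drops to about 23 on the interval in section 1.4, so a fixed minimum of 28 should not be read into the documents.

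Direction and size are undetermined. The move from 5% to 13% rejection is a scenario that depends on an assumed 0.30 log2 bias, the back-solved SD, 15 versus 20 subjects and a two-sided 0.05 test. Given the exploratory purpose and the low cost of the remedy, this is a should-fix.

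**What to change.** - **Sections 4 and 6.2:** frequency-match controls to the enrolled Cohort 1 on broad age or birth-year strata, for example born by 1968 versus later. With 12-15 subjects in Cohort 1, finer bands would be too sparse.
- **Section 10.4:** analyse log fold rise with a linear model on cohort, adjusted for age or birth cohort. Add a sensitivity analysis restricted to the age range in which the cohorts overlap.
- **Section 4.1, criterion 7:** state that naïve means vaccine-naïve.
- **Sections 1.4 and 6.2:** reconcile the five-to-ten-year interval with the 2005-2009 dates.

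**Cost.** Control recruitment slows somewhat, because it has to follow the ages enrolled in Cohort 1. If ages remain imbalanced, adjustment loses some precision: power is 71% when cohorts differ by 1 SD in age and age is unrelated to response. Restriction gives about 74% with 15 versus 15. Matching first keeps both losses small. If controls are already enrolled, the two analysis changes can still be made, since age is needed for eligibility and is therefore available.
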